1 STUDY DETAILS

This statistical analysis plan (SAP) outlines the analyses to be generated for the global clinical study report (CSR). Additional analyses required for regional submissions will be prespecified in a separate analysis plan and will be submitted to the appropriate authorities.

Table 1 Objectives and Endpoints

[figure not shown]
Objectives	Estimand description / Endpoints
Primary	
To compare the clinical efficacy of benralizumab 30 mg with placebo in patients with AD despite treatment with topical medications ^a .	
 • Population: Full analysis set • Endpoint: A binary response giving the proportion of patients with an IGA 0/1 and a decrease in IGA of ≥ 2 points at Week 16 relative to baseline • Intercurrent events: Patients who withdraw from the study will be considered as non-responders from the time of withdrawal up to Week 16. Patients who require rescue therapy from Day 29 up to Week 16 will be considered as non-responders from the time of this rescue use up to Week 16. • Summary measure: Odds ratio and difference in proportions between benralizumab and placebo at Week 16
Secondary	
To compare the effect of benralizumab with placebo on supportive measures of clinical efficacy in patients with AD despite treatment with topical medications ^a .	
 • Key secondary endpoint ^c: proportion of patients with skin clearance (EASI-75) at Week 16 • Key secondary endpoint ^c: proportion of patients with an improvement of ≥ 4 points in peak pruritus weekly score at Week 16 • Key secondary endpoint ^c: proportion of patients with skin clearance (EASI-90) at Week 16 • Proportion of patients with skin clearance (EASI-50) at Week 16 • Proportion of patients with skin clearance (EASI-100) at Week 16 • Change from baseline in EASI score at Week 16 • Change from baseline in peak pruritus score at Week 2 • Change from baseline in POEM score at Week 16 • Change from baseline in SCORAD at Week 16
To compare benralizumab with placebo on patient-reported health-related quality of life measures in patients with AD despite treatment with topical medications ^a .	
 • Change from baseline in DLQI and CDLQI at Week 16
To estimate the PK and immunogenicity of benralizumab 30 mg in in patients with AD despite treatment with topical medications ^a .	
 • Serum benralizumab concentration • ADA

Table 1 Objectives and Endpoints

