1.1.2 Investigational Product Dosing Regimen

Participants who meet entry criteria will be randomized 1:1:2 by the interactive voice/web response system (IxRS) to 1 of the 3 treatment sequences described in Section 1.1.

Blinded IP (benralizumab or placebo) will be administered Q4W at Weeks 0, 4, 8, and 12 (Figure 1).

From Week 16 onwards, participants initially randomized to benralizumab 30 mg will receive benralizumab 30 mg Q4W or Q8W interval, according to their original randomization at Visit 2 (Week 0) (Figure 1).

At Weeks 16, 20, and 24, participants initially randomized to placebo will receive benralizumab 30 mg Q4W. At Week 28, these participants will transition to receive benralizumab 30 mg Q8W interval (Figure 1).

All participants on Q8W regimen from Week 16 onwards will continue to receive treatment containing placebo at their Q4W visit intervals (Figure 1), thus maintaining the blinded treatment regimen.

The final dose of benralizumab or placebo will be administered at Week 48.

Please refer to the clinical study protocol (CSP) for more details.

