1.2 Number of participants

Approximately 270 participants are expected to be enrolled/screened in order to achieve at least 160, and a maximum of 200, eligible study participants randomly assigned to study intervention to ensure that a broad distribution of participants is recruited across the range of ages and blood eosinophil levels to allow potential identification of responding subpopulations and appropriate cut-offs for future studies, if necessary.

Randomization will be stratified by blood eosinophils (< 300 cells/ μ L, ≥ 300 cells/ μ L) collected at screening and age at screening (≥ 12 to < 18 years and ≥ 18 years). Participants will be randomized in minimum cohort sizes across the baseline blood eosinophil and age subgroups; the intended distribution of participants in total across the treatment groups for each combination of these factors is summarized in Table 2. If the minimum recruitment target in any cohort is achieved, that cohort may remain open in order to fulfil minimum recruitment targets for the remaining cohorts. Thus, minimum recruitment targets may be exceeded in cohorts that remain open while fulfilling recruitment targets for other cohorts. Recruitment will stop when a maximum of 200 participants in total is achieved.

Table 2 Number of Participants Randomized by Stratification Factors

	Baseline blood eosinophils	
	<300 cells/ μ L	\geq 300 cells/ μ L
Adolescents (\geq 12 to < 18 years), n	20	30
Adults (\geq 18 years), n	40	70

For the primary analysis in the overall population, a minimum of 80 participants per treatment group will provide a high level of power (> 95%) to detect a 30% difference between benralizumab 30 mg Q4W and placebo for the primary endpoint. This calculation is based on a 2-sided test and a 5% significance level and assumes a response rate of 40% for benralizumab 30 mg Q4W and 10% for placebo.

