3.1.3 Visit windows

For the Peak Pruritus NRS, weekly summary scores will be calculated using the 7 daily scores for each week, starting with randomization day (e.g. Days 1 to 7 for Week 1, Days 8 to 14 for Week 2), regardless of visit attendance days.

For Peak Pruritus NRS Week 16 score, the 7 days prior to the scheduled Week 16 timepoint (ie Days 106 to 112) will be used for calculation. However, only days prior to the first dose of IP in the extension period will be used for the Week 16 score derivation. If the Week 16 visit, and therefore the start of extension period IP dosing, occurs ahead of schedule (ie at Day 112 or earlier), then the 7 days prior to this day of first dose of extension period IP will be used for the Week 16 score, and the Week 15 score will be set to missing. If the Week 16 score cannot be calculated on the 7 daily scores, then an additional 1-day shift to assess the 8 daily scores before extension IP dose day will be assessed, and the Week 15 score will be set to missing. For Week 17 score, the scheduled 7 days before day 120 (ie Days 113-119) will be used. If the Week 16 visit occurs at Day 113 or later, Days 106 to 112 will be used in the Week 16 score as planned. Further details on scoring for daily Peak Pruritus NRS will be provided in Section 3.3.2.

For efficacy endpoints that present visit-based data, visit windows will be applied. The adjusted analysis-defined windows will be based on the collection schedule listed in the protocol and variables will be windowed to the closest scheduled visit for that variable.

Visit windows following baseline will be constructed in such a way that the upper limit of the interval falls halfway between two visits (the lower limit of the first post-baseline visit will be study day 2). If an even number of days exists between two consecutive visits, then the upper limit will be taken as the midpoint value minus 1 day. Visit windows are constructed so that every observation collected can be allocated to a particular visit. No visit windows will be defined for screening visits.

For assignment of data to adjusted analysis-defined visit windows, study day will be defined as follows:

$$(Date\ of\ assessment - date\ of\ randomization) + 1$$

Following this definition, for example if the day of randomization is study day 1 and date of assessment is the planned date of Visit 3 (Week 4), the study day will be 29 (28+1).

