3.1.5 Intercurrent Events

Intercurrent events are withdrawal from the study at any time or requiring rescue therapy from Day 29 onwards. However, participants who started on placebo and switched to benralizumab in the extension phase are additionally permitted rescue therapy for 28 days from starting benralizumab, and thus additionally any rescue therapy use from Day 141 (ie 29 days after first dose of benralizumab) onwards will be considered as intercurrent event for these participants.

Withdrawal from the study will be considered from the day after withdrawal onwards, thus data on the day of withdrawal will be used as recorded. Rescue therapy from Day 29 (of first dose, and additionally for placebo-benralizumab participants from first benralizumab dose) onwards will be considered for intercurrent event imputation from the day of taking rescue medication onwards.

For responder or binary analyses, participants with intercurrent events will be considered as non-responders from the time these events occur. Participants with missing data for binary endpoints will also be considered non-responders at affected post baseline visits. Intercurrent events will be considered for analyses and descriptive summaries.

For change from baseline analyses or number and percentage of score category summaries, participants with intercurrent events will be considered as having missing scores from the time these events occur. Intercurrent events will be considered for analyses and descriptive summaries.

For summaries of number and percentage of individual questionnaire scores, all data will be presented as recorded, without imputation for intercurrent events.

The categorisation and imputations of responder status and reasons for non-response are provided in following table.

Table 3 Response Category Imputations

Response Category	Imputation Rule
Responder	Keep data as recorded, unless after taking rescue medication
Non responder	
Recorded as non-responder	Keep data as recorded, even if after taking rescue medication

Table 3 Response Category Imputations

Response Category	Imputation Rule
Missing	For missing questionnaire/visit, where participant remains in study and could be Responder or Recorded Non-responder or Rescue medication and remain in study
Rescue medication and remain in study	Impute if recorded as Responder and participant ongoing in study. Impute from day of rescue medication onwards, but only for assessments where participant is a Recorded Responder

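### Week 16 IGA and EASI non-response is imputed by the date of the windowed assessment, so a response recorded shortly before withdrawal or rescue can stand against the primary estimand

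*SAP*

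**What the plan says.** **Estimand.** For withdrawal, Table 1 of the SAP states: "Patients who withdraw from the study will be considered as non-responders from the time of withdrawal up to Week 16". It treats rescue from Day 29 in the same way. Table 11 lists both events as non-response, and Section 4.2.6.1 repeats that they count as failure from the event up to Week 16. The key secondary endpoints, including EASI-75 and EASI-90, use the same estimand.

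**Windows.** Section 3.1.3 sets each boundary halfway between scheduled visits and adds: "Visit windows are constructed so that every observation collected can be allocated to a particular visit". If a window holds several values, the one closest to the scheduled day is used, so a single early value is used by default.

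**Timing of events.** Section 3.1.5 lets withdrawal take effect only on the following day: "thus data on the day of withdrawal will be used as recorded". Table 3 leaves a recorded response alone unless it falls after rescue, and its two withdrawal rows apply only to assessments after withdrawal.

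**The concern.** The estimand is keyed to a time point: what happened up to Week 16. The derivation is keyed to a date: whether the assessment placed in the Week 16 window came before or after the event. The two agree when that assessment is the Week 16 visit itself. They disagree when it is an earlier assessment, the event follows it (or withdrawal falls on the same day), and nothing later is recorded. The derivation then gives a responder where the estimand gives a non-responder.

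This concerns the primary endpoint and the EASI responder endpoints. The SAP assumes that recorded responders are commoner on benralizumab, so the errors need not cancel between arms. Two programmers following the text in good faith could also score the same participant differently.

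**Working it through.** **The plan's own figure.** The SAP prints no day limits for the Week 16 window. Its nearest printed figure is the power in Section 1.2: above 95% with 80 per group, where the calculation "assumes a response rate of 40% for benralizumab 30 mg Q4W and 10% for placebo" at two-sided 5%.

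- Power = Φ{[|p1 − p2|√n − 1.96√(2p̄(1 − p̄))] / √[p1(1 − p1) + p2(1 − p2)]}, with p1 = 0.40, p2 = 0.10, p̄ = 0.25, n = 80.
- = Φ[(2.683 − 1.200) / 0.574] = Φ(2.58) = 99.5%. Fisher's exact test gives 99.3%. The stated figure is reproduced.

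**Where the window opens.** Inputs: the day convention of Section 3.1.3 (for Week 4, "the study day will be 29 (28+1"), so Week w is Day 7w + 1; and visits every four weeks (Section 1.1.2: IP "will be administered Q4W at Weeks 0, 4, 8, and 12"). Assumption: IGA and EASI are collected at Week 12. Their schedule is in the protocol, which is not at hand.

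- Week 12 = 7 × 12 + 1 = Day 85; Week 16 = 7 × 16 + 1 = Day 113.
- Midpoint = (85 + 113)/2 = Day 99.
- If the 28-day gap counts as even, the Week 12 window ends on Day 98 and Week 16 opens on Day 99, 14 days early.
- If the 27 days strictly between the visits are counted (odd), Week 16 opens on Day 100, 13 days early.
- If the preceding assessment were Week 8 (Day 57), the midpoint would be (57 + 113)/2 = Day 85, and the window would be wider.

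**When an assessment would fall there.** Section 1.1.1 places the treatment-discontinuation (IPD) visit 4 weeks ± 7 days after the last dose. With doses on their nominal days:

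- Last dose at Week 12 (Day 85): visit on Days 106 to 120.
- Last dose at Week 8 (Day 57): visit on Days 78 to 92, before the window opens.

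So an on-time IPD visit reaches the early part of the window only on Days 106 to 112. Days 99 to 105 need a late or unscheduled assessment.

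**Two cases** (assuming IGA is assessed at the IPD visit):

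| Case | Under 3.1.3, 3.1.5 and Table 3 | Under Tables 1, 11 and 4.2.6.1 |
|---|---|---|
| IGA response at IPD visit on Day 108; leaves the study that day | In window, not after withdrawal: responder | Non-responder |
| IGA response at IPD visit on Day 106; telephone follow-up only; rescue reported for Day 110 | In window, before rescue: responder | Non-responder |

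The second case is possible because the telephone option in Section 1.1.1 collects concomitant medication but no IGA.

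**Size.** The SAP gives no withdrawal rate. Assumption: 10% to 15% of 160 withdraw before Week 16, evenly over 112 days.

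- Withdrawals: 16 to 24. Share on Days 99 to 112: 14/112 = 12.5%. In-window withdrawals: 2 to 3.
- Average response at the design rates: (40% + 10%)/2 = 25%. Expected responders among them: 0.25 × 2 = 0.5 to 0.25 × 3 = 0.75, over both arms.
- One participant in an arm of 80: 1/80 = 1.25 percentage points.

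The 0.5 to 0.75 is before requiring that an assessment fell in the window. Rescue cases would add to it; the document gives nothing from which to count them.

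**The case against.** The strongest reply is that the plan already gives the intended answer. Section 4.2.6.1 states the rule up to Week 16, Section 4.1 scores missing visits and data after withdrawal as non-response, and the text below Table 3 keeps a withdrawn participant in the imputed category. This does not settle the matter. That category is defined for assessments after withdrawal, whereas the value at issue was recorded on or before it, and the explicit rule for the day of withdrawal points the other way. What stands is that the documents lack a precedence rule. They do not state outright that the window overrides the estimand.

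A second reply is that keeping data from the day of withdrawal is a deliberate, prespecified choice. It is reasonable for a Week 16 visit held early, and the fix should preserve it.

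Third, the circumstances are unusual, and this stands. A reader might infer that anyone leaving two weeks early is liable to be counted as a responder. The IPD schedule does not support that for Days 99 to 105. An IPD visit is also not a withdrawal: treatment discontinuation is handled by treatment policy, so the participant must leave the study as well. Rescue soon after a near-clear IGA will be uncommon. If a Week 16 visit takes place near Day 113, it is normally the value used, and a response recorded after rescue is then imputed as non-response.

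**Conclusion.** The inconsistency is real for the binary IGA and EASI endpoints: the stated derivation can score as a Week 16 responder someone whom the primary estimand makes a non-responder. It rests on IGA and EASI being collected at Week 12 and at the IPD visit; without a Week 12 assessment the window would only be wider.

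The size is small. A reader might take the 2 to 3 in-window withdrawals as the number misclassified. Only those with a response recorded in the window count, so on the assumed withdrawal rates well under one participant is expected over both arms. The stated power is not in question: even four placebo participants wrongly scored as responders (10% + 4/80 = 15%, against 40%) would leave about 95.0%.

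A reader might also infer the same fault in the continuous endpoints. The documents do not support that: Section 4.1 and Appendix 8.1.3 keep data up to the event and treat only later data as missing, so a value recorded before the event is valid for the MMRM. The pruritus responder endpoint has its own Week 16 rule (Days 106 to 112) and is outside this point.

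The reason to act is that the primary endpoint should have one derivation, fixed before unblinding.

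**What to change.** Add to Section 3.1.5 and Table 3, for the binary IGA and EASI endpoints only: a participant who withdrew, or used rescue from Day 29, before the Week 16 visit (or before Day 113 if no Week 16 visit took place) is a non-responder at Week 16, whatever earlier assessment falls in the window. State that a genuine Week 16 visit held early, with withdrawal on the same day, is kept as recorded. Leave the continuous endpoints unchanged.

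The cost is a short addition to the SAP and one derivation flag. The small downside is that a few early in-window responses no longer count at Week 16.

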3.1.4 Prior/concomitant medications

Medications will be categorized according to the WHO Drug Reference List dictionary which employs the Anatomical Therapeutic Chemical (ATC) classification system.

A medication will be regarded as prior if it was stopped on or before the date of randomization (medication stop date \leq date of randomization).

A medication will be regarded as ‘concomitant’ if the start date is on or after the date of randomization or if it started prior to the date of randomization and was ongoing after the date of randomization. If a medication was started and stopped on the date of randomization, it will be considered as concomitant.

Concomitant medications for the 16-week placebo-controlled analysis reporting will include all concomitant medications with start date prior to entering the extension period.

Concomitant medications for the Week 52 end of study reporting over the entire study duration will include all concomitant medications. Concomitant medications reported for the extension period alone are those with start date after entering the extension period, and those ongoing from the 16-week placebo-controlled period.

The handling of partial/missing dates for assigning prior/concomitant medications is detailed in Appendix 8.3. Duration of prior/concomitant medications will not be calculated using imputed dates and will instead be set to missing. No other medication data will be imputed.

Throughout the study, participants will be required to maintain stable doses of their topical moisturizer for AD (CSP Section 6.5.1). If medically necessary for intolerable AD symptoms

that occur during the study, rescue therapy may be prescribed to participants at the discretion of the Investigator. For more detail see CSP Section 6.5.3.

Medication data will be presented for both, the 16-week placebo-controlled treatment period and the Week 52 reporting.

3.1.5 Intercurrent Events

Intercurrent events are withdrawal from the study at any time or requiring rescue therapy from Day 29 onwards. However, participants who started on placebo and switched to benralizumab in the extension phase are additionally permitted rescue therapy for 28 days from starting benralizumab, and thus additionally any rescue therapy use from Day 141 (ie 29 days after first dose of benralizumab) onwards will be considered as intercurrent event for these participants.

Withdrawal from the study will be considered from the day after withdrawal onwards, thus data on the day of withdrawal will be used as recorded. Rescue therapy from Day 29 (of first dose, and additionally for placebo-benralizumab participants from first benralizumab dose) onwards will be considered for intercurrent event imputation from the day of taking rescue medication onwards.

For responder or binary analyses, participants with intercurrent events will be considered as non-responders from the time these events occur. Participants with missing data for binary endpoints will also be considered non-responders at affected post baseline visits. Intercurrent events will be considered for analyses and descriptive summaries.

For change from baseline analyses or number and percentage of score category summaries, participants with intercurrent events will be considered as having missing scores from the time these events occur. Intercurrent events will be considered for analyses and descriptive summaries.

For summaries of number and percentage of individual questionnaire scores, all data will be presented as recorded, without imputation for intercurrent events.

The categorisation and imputations of responder status and reasons for non-response are provided in following table.

Table 3 Response Category Imputations

Response Category	Imputation Rule
Responder	Keep data as recorded, unless after taking rescue medication
Non responder	
Recorded as non-responder	Keep data as recorded, even if after taking rescue medication

Table 3 Response Category Imputations

Response Category	Imputation Rule
Missing	For missing questionnaire/visit, where participant remains in study and could be Responder or Recorded Non-responder or Rescue medication and remain in study
Rescue medication and remain in study	Impute if recorded as Responder and participant ongoing in study. Impute from day of rescue medication onwards, but only for assessments where participant is a Recorded Responder
Rescue medication and withdrawn from study	For participants who have taken rescue medication before withdrawal. Impute for post-withdrawal assessments
No rescue medication and withdrawn from study	For participants who have Not taken rescue medication before withdrawal. Impute for post-withdrawal assessments

Participants can move between different visits between categories of Responder, Recorded Non-responder and Missing. Participants can move between different visits between categories of Recorded Non-responder, Missing and Rescue medication and remain in study. After a participant has withdrawn, they will stay in the imputed withdrawal category.

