Any assessments performed after entering the extension period (ie the day after first dose of IP in the extension period at Week 16 visit) will be assigned to visit windows in the extension period and will not be assigned to visit windows in the 16-week placebo-controlled treatment period. Assessments at Week 16 visit will be assigned to Week 16.

If multiple assessments are recorded within a single adjusted visit window, please refer to the rules below:

- If there are 2 or more observations within the same visit window, then the non-missing observation closest to the scheduled study day will be used in the analysis.

- If 2 observations are equidistant from the scheduled study day, then the non-missing observation with the earlier collection date will be used in the analysis.
- If 2 observations are collected on the same day then the non-missing observation with the earlier collection time will be included in the analysis.

If a visit window does not contain any observations, then the data will remain missing.

For endpoints which are not collected at every visit (including PROs with recall periods of 1 week or more), the above rules will be applied to derive adjusted analysis-defined visit windows based on the protocol defined visit schedule for that endpoint.

Similarly, visit windows will be applied for laboratory parameters. Vital signs will be based on the case report form (CRF) visit designation.

When IP dosing needs to be postponed, it is recommended that all scheduled treatment visit procedures (except for IP administration) are still performed within the visit window. For further details see CSP Section 6.1.2.

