4.2.7.3 Change from baseline in EASI score

The secondary endpoint of change from baseline in EASI score will be analyzed by a MMRM model at Week 16.

The model will include change from baseline in EASI score as the dependent variable (derived for each participant and every scheduled visit up to Week 16); baseline EASI score as a continuous covariate; treatment, age at screening (≥ 12 to < 18 years/ ≥ 18 years), blood eosinophils at screening (< 300 cells/ μ L; ≥ 300 cells/ μ L), and visit as categorical factors; and treatment-by-visit as an interaction term. The strata variables will be used as recorded on the database. An unstructured variance-covariance matrix will be used to model within-subject errors, and the Kenward-Roger approximation will be used to estimate denominator degrees of freedom and to adjust standard errors, the OBSMARGINS option will be used to derive the LSMEAN estimates assuming mean values for the baseline covariates. If the model fails to converge, alternative variance-covariance models will be tried in the following order: Toeplitz, first-order regressive, compound symmetry.

For each visit, the model will be used to estimate the mean change from baseline for each treatment group (benralizumab 30mg Q4W and placebo) and difference between treatment groups, with corresponding 95% CIs and the p-value, corresponding to a 2-sided test.

The distributional assumptions of the MMRM model will be checked by examining plots of residuals. If the residuals suggest that it is unreasonable to assume that data follow a Normal distribution (eg, data are skewed and the constant variance assumption is not met), alternative models will be explored. For example, data may be log transformed prior to fitting the model, or a non-parametric method may be deemed more appropriate.

The observed means and mean changes from baseline will be summarized using descriptive statistics by treatment group and each scheduled visit up to Week 16.

Additional sensitivity analyses based on different missing data mechanism assumptions may be used to explore the robustness of any treatment effect, including

- Participants with rescue therapy use (from Day 29 onwards) will be imputed using LOCF approach and analyzed with analysis of covariance (ANCOVA);
- Treatment policy approach where all available data is included regardless of rescue use, and analyzed with MMRM;

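### SAP 3.1.5 sets visit scores to missing from the calendar day rescue is taken, including scores recorded before rescue, so the score that prompted rescue can drop out of the continuous analyses

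*SAP*

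**What the plan says.** Section 3.1.5 gives its two intercurrent events different starting points. Withdrawal takes effect the day after it occurs, "thus data on the day of withdrawal will be used as recorded". Rescue from Day 29 "will be considered for intercurrent event imputation from the day of taking rescue medication onwards". For change-from-baseline analyses, "participants with intercurrent events will be considered as having missing scores from the time these events occur". There is no exception for an assessment made earlier on the day rescue was taken.

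Other parts of the SAP are worded differently:

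- Section 4.1 treats as missing the data that come after rescue use from Day 29.
- Appendix 8.1.3 does the same, but refers to rescue after Day 29 rather than from Day 29.
- In Table 3, the responder row keeps a value unless it follows rescue. The row for rescue users who stay in the study starts imputation on the day of rescue. For recorded non-responders the rule is "Keep data as recorded, even if after taking rescue medication".

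The main analysis of the continuous endpoints is an MMRM by direct likelihood under a missing-at-random assumption (Section 4.2.7.3, Appendix 8.1.3).

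**The concern.** Section 3.1.4 allows rescue "If medically necessary for intolerable AD symptoms", at the investigator's discretion. A poor score and a rescue start on the same visit day are therefore foreseeable. The score taken before rescue is not affected by it and is often the reason for it. Under Section 3.1.5 that score is deleted, and the model sees only the better values from earlier visits.

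A missing-at-random analysis can tolerate loss of everything after rescue if the score that predicts rescue is in the data. Once that score is removed, the chance of being missing depends on an unobserved value, and the plan's own rule breaks the assumption. The secondary change-from-baseline endpoints at stake are EASI, SCORAD, POEM, DLQI and CDLQI. Rescue that starts at the Week 16 visit can remove the endpoint value itself.

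The planned sensitivity analyses do not reliably expose this. In one, "Participants with rescue therapy use (from Day 29 onwards) will be imputed using LOCF approach"; under the day-of rule it carries forward the visit before the flare. The dropout-reason imputation in Appendix 8.1.4 is keyed to reasons for study withdrawal, not to rescue. The treatment-policy MMRM would keep the score, but it is optional and answers a different question.

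**Working it through.** **Plan's own figure.** The SAP states no rescue rate, no EASI variance and no power for a continuous endpoint, so no figure on this point can be reproduced.

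**Same-day case, side by side.** Take an EASI done before rescue on the visit day, with rescue taken later that day.

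- Section 3.1.5: missing.
- Section 4.1 and Appendix 8.1.3: kept, if *after* is read by time.
- Withdrawal on that day instead of rescue: kept.
- Section 3.1.1, for the comparable question of first dosing: an untimed assessment on the dosing day is assumed to come before the dose.

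Two programmers could build different datasets from this text. Day 29 is also the planned Week 4 visit (Section 3.1.3), so the difference between *from* and *after* Day 29 matters for rescue taken at that visit.

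**Size.** A large-sample simulation used 200,000 per arm, with visits at Weeks 4, 8, 12 and 16. All of the following inputs are assumptions:

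- EASI-like score with mean 30, SD 12 and within-person correlation 0.6.
- Placebo change of -4, -6, -7 and -8 at the four visits.
- Treatment difference phased in at 40%, 70%, 90% and 100% of its Week 16 value.
- Rescue triggered when a visit score exceeds a threshold: 40 or 36 in both arms, or 34 or 30 for benralizumab against 40 for placebo.
- 25%, 50% or 100% of rescue taken on the visit day itself; the rest starts later, so that visit's score is kept under either rule.

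Each visit was regressed on arm and all earlier scores among those still observed, and the means were propagated to Week 16. With monotone missingness this matches a baseline-adjusted unstructured MMRM. The age and eosinophil strata were left out. Bias = estimate minus true difference; negative differences favour benralizumab.

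| True difference | Rescue, placebo vs benralizumab | Day-of rule at 25% / 50% / 100% | Same-day score kept |
|---|---|---|---|
| -6 | 22% vs 13% | -5.81 / -5.67 / -5.33 | -5.97 / -6.00 / -6.02 |
| -6 | 34% vs 23% | -5.80 / -5.51 / -4.98 | -6.00 / -5.95 / -5.96 |
| 0 | 22% vs 22% | 0.01 / 0.00 / 0.03 | 0.01 / 0.00 / 0.02 |
| -6 | 22% vs 28% | -6.04 / -6.14 / -6.39 | -5.97 / -6.01 / -6.04 |
| -6 | 22% vs 42% | -6.23 / -6.55 / -7.31 | -5.97 / -6.02 / -5.97 |

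- Placebo rescued more: bias from -5.81 - (-6) = 0.19 to -4.98 - (-6) = 1.02. This is 0.19/6 = 3% to 1.02/6 = 17% toward zero.
- Benralizumab rescued more: bias from -6.04 - (-6) = -0.04 to -7.31 - (-6) = -1.31, away from zero.
- Equal rescue and no true effect: essentially none.
- Keeping the same-day score stays within about 0.05 of the truth throughout.

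In these runs the estimate moves in favour of whichever arm uses more rescue.

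A second simulation had 80 per arm, baseline EASI 28 (SD 10), a true difference of -6.0 and all rescue starting at visits. With placebo rescued more, it gave -5.64 to -5.11 under the day-of rule and about -6.0 with the score kept.

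**Scale.** With SD 12 and 80 per arm, the unadjusted standard error is 12 × √(2/80) = 1.90. A bias of 0.2 to 1.0 is therefore about 0.1 to 0.5 standard errors.

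**The case against.** The strongest reply is that the consequence is modest and partly covered by other text.

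- **Scope.** The affected endpoints lie outside the testing hierarchy (Section 4.1.1) and carry nominal p-values. This stands.
- **Frequency.** The rule turns on the day rescue is taken, not prescribed, so a prescription at the visit with first use the next day loses nothing. This stands. It is why the share of rescue on visit days was varied; at 25% the shift with placebo rescued more is only about 0.2 points.
- **Other wording.** Section 4.1 and Appendix 8.1.3 can be read as keeping the score. They can, but Section 3.1.5 is the explicit operational rule, so the conflict remains.
- **Diary data.** Peak pruritus is recorded each evening with 24-hour recall (Section 3.3.2), so a rescue-day entry probably reflects rescue in part. A day-of rule is sensible there, and a blanket day-after rule would not be. This stands and shapes the fix.

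A reader might infer that the binary endpoints are damaged too. The SAP does not support that for the primary and key secondary endpoints. A flare is already a recorded non-response, which Table 3 keeps. Harm needs a recorded responder who takes rescue for intolerable symptoms the same day, which is implausible for IGA 0/1, EASI-75 or EASI-90. The Week 16 pruritus score uses Days 106 to 112, or days before the first extension dose (Section 3.1.3), so rescue starting at that visit does not reach it. Some effect on EASI-50 is conceivable but not shown.

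A reader might also infer that the rule plainly erases the Week 16 score of a placebo participant who starts benralizumab and rescue that day. The text does not settle this: "Assessments at Week 16 visit will be assigned to Week 16", while switchers are "additionally permitted rescue therapy for 28 days from starting benralizumab".

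**Conclusion.** The point holds in limited form. As written, Section 3.1.5 discards visit scores taken before rescue on the same day. That conflicts with Section 4.1 and Appendix 8.1.3, differs from the withdrawal rule, and undermines the missing-at-random assumption of the secondary change-from-baseline analyses. It matters only for rescue from Day 29 taken on an assessment day. The Week 2 pruritus endpoint falls earlier, so its score is not removed.

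It is tempting to conclude that the rule must dilute the benralizumab effect. The SAP gives no rescue rates by arm, so that direction is conditional. It is likely if the drug works and rescue is triggered alike in both blinded arms. If benralizumab used more rescue, a true benefit would be exaggerated. The sizes rest wholly on the assumed score distribution, rescue thresholds and share of rescue on visit days; they indicate scale and do not predict this trial.

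**What to change.** Reconcile Section 3.1.5, Table 3, Section 4.1 and Appendix 8.1.3 before unblinding:

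- For on-site visit assessments, keep as recorded any score obtained before first rescue intake on the same day. Decide by clock time where both times exist. Otherwise assume that visit assessments came before rescue started that day, as Section 3.1.1 does for dosing. Say that this includes the Week 16 visit.
- Keep the day-of rule for the evening peak pruritus diary.
- Run the present day-of rule for visit scores as a sensitivity analysis, so that its influence can be seen.
- Use one form, from or after Day 29, throughout.

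This changes data handling only, not who may receive rescue. The cost is a few sentences, the affected rows of Table 3, a changed date and time comparison in programming, and one extra set of model runs. The downside is small: where times are missing, an occasional same-day score taken after rescue will be kept.
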